5.1 Regadenoson Screening Procedures

- ✓ Vital signs, height and weight
- ✓ Documentation of pain score prior to lab draw
- ✓ Blood Tests:
 - Complete blood count with or without differential & platelet count
 - Comprehensive metabolic panel
 - Coagulation tests
 - Study lab draw for Definity complement deposition and values (optional)
- ✓ Urine pregnancy test (in women of childbearing potential)

- ✓ Collect demographics, race, ethnicity, medical diagnostic history
- ✓ Concomitant medications reviewed
- ✓ Determine caffeine and theophylline will not be taken 12 hours prior to receiving regadenoson (infusion can be delayed for 12 hours if the subject ingests caffeine or theophylline)
- ✓ Determine dipyridamole and aminophylline will not be taken in the 48 hours prior to regadenoson infusion
- ✓ A study physician or designee may read and assess a cardiac EKG tracing to rule out 2° or 3° heart block prior to the administration of regadenoson. A recent (≤30 days) EKG may also be used for the same purpose, if it is available.

5.2 Sickle Cell CEU Subject Screening Procedures

- ✓ Vital signs, height and weight
- ✓ Urine pregnancy test in all women of childbearing potential
- ✓ Collection of demographics, race, ethnicity, medical diagnostic history and medication history

5.3 Healthy Control Subjects Screening Procedures

- ✓ Sickledex blood test
- ✓ Collection of demographics, race, ethnicity, medical diagnostic history and medication history
- ✓ Urine pregnancy test in all women of childbearing potential

5.4 Technique Optimization Control Subjects Screening Procedures

- ✓ Collection of medical diagnostic history and medication history
- ✓ Physical exam, if subject's medical history suggests possible cardiac disorders requiring further assessment, or per study physician's discretion

5.5 Sickle Cell Control Subjects Screening Procedures

- ✓ Collection of demographics, race, ethnicity, medical diagnostic history and medication history
- ✓ Vital signs, height and weight
- ✓ Urine pregnancy test in all women of childbearing potential
- ✓ Collection of demographics, race, ethnicity, medical diagnostic history and medication history

6. On-Study Procedures

6.1 Regadenoson (Within 4 hours prior to infusion)

- Signal Averaged ECG (+/- 30 days from infusion visit date / Baseline)

- Reconfirm eligibility and that subject is at baseline (if necessary)
- Concomitant medication use reviewed prior to infusion:
 - Assess caffeine and theophylline intake for previous 12 hours (delay the onset of the infusion for at least 12 hours if the subject recently ingested caffeine or theophylline)
 - Assess dipyridamole and aminophylline intake in previous 48 hours.
- Limited functional 2D echocardiogram prior to infusion
- Contrast-enhanced ultrasound is performed prior to infusion
- Documentation of pain score prior to lab draw
- Correlative laboratory studies and optional “red and white blood cell” exploratory study labs (up to 6ml) are drawn prior to infusion
 - *If subject agrees, and gives the Definity complement sample, “red and white blood cell” samples may only be collected if at least +/-8 weeks from Definity complement sample being drawn (as not to exceed 50ml blood collected in 8 week period)
- Complete cardiac questionnaire (can be completed any time prior to the end of observation period)

Regadenoson Administration Procedure:

Prior to starting the study drug infusion, a baseline heart rate and blood pressure will be established with at least 2 measurements, 5-10 minutes apart. If the last two consecutive measurements have a difference greater than 5 beats per minute (heart rate) or 10 mm Hg (systolic blood pressure), they should be repeated every 5 minutes until they stabilize. The baseline measurement is the last heart rate and blood pressure measurement prior to study drug infusion. Oxygen saturation and heart rate will be measured during drug infusion and blood pressure will be taken every 30 minutes for 2 hours (+/-10 minutes), hourly for the next 2 hours, then every two hours (+/-15 minutes) for the duration of the infusion, and during the observation period.

Blood draws will be performed prior to infusion and at the times contrast-enhanced ultrasound is performed, for laboratory measurements. Pain will be assessed at the same time as blood draws using a standardized pain scale. Blood pressure monitoring and blood draws will be performed on a limb or site other than the regadenoson infusion.

The infusion will be stopped for any for any toxicity that is designated a serious adverse event (SAE). For this study, an SAE will be defined according to the CTEP Active Version of the NCI Common Terminology Criteria for Adverse Events (CTCAE) with the exception of heart rate and blood pressure. SAEs are CTCAE grade 3 events as well as significant changes in heart rate or blood pressure (defined in **section 11.3**). Before initiation of the regadenoson infusion, resuscitation equipment and trained staff will be available.

After the 24 hour infusion (or if the infusion is stopped early for an SAE), there will be a 6 hour observation period during which the subject will be monitored. Oxygen saturation and heart rate will be measured, blood pressure will be recorded every 2 hours (+/-15 minutes) and blood samples will be collected at the end of the observation period at 30 hours. Caffeine may not be ingested during the infusion or observation period.

Regadenoson (6 hours after infusion start +/- two hours, or earlier if necessary, per discretion of study physician)

- Contrast-enhanced ultrasound
- Documentation of pain score prior to lab draw
- Correlative laboratory studies drawn

Regadenoson (24 hours from infusion start within two hours before infusion stop, or earlier if necessary, per discretion of study physician)

- Limited functional 2D echocardiogram
- Contrast-enhanced ultrasound
- Documentation of pain score prior to lab draw
- Correlative laboratory studies and optional exploratory study labs (up to 6ml) ardrawn
- Infusion may over-run up to 1 hour, with PI permission (if difficulty completing study procedures before infusion stopped)
 - *If subject agrees, and gives the Definity complement sample, “red and white blood cell” samples may only be collected if at least +/-8 weeks from Definity complement sample being drawn (as not to exceed 50ml blood collected in 8 week period)

Regadenoson (30 hours from infusion start +/- two hours, or earlier if necessary, per discretion of study physician)

- Contrast-enhanced ultrasound
- Documentation of pain score and adverse events, if applicable
- Correlative laboratory studies drawn

Post-regadenoson follow-up period (30 days post infusion)

- Subjects will be contacted by phone weekly (plus or minus 3 days) for 4 weeks following the conclusion of regadenoson therapy to assess for any potential toxicities related to study drug

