3.1 Regadenoson Eligibility Criteria

Regadenoson Study Treatment Inclusion Criteria:

1. Diagnosis of sickle cell disease confirmed by hemoglobin analysis
2. Ages 18 to 70 years
3. Laboratory parameters:
 - a. Hemoglobin \geq 6 g/dL
 - b. Platelets \geq 150,000/mcL
 - c. ALT \leq 2.5 X upper limit of normal
 - d. Serum creatinine < 1.5 mg/dL
 - e. INR < 1.5
 - f. PTT < 40 seconds
4. Reliable IV access as determined by physician

Regadenoson Study Treatment Exclusion Criteria:

1. Subject is not at baseline (see definition of baseline **section 3.7**) at the time of study treatment
2. Current physician diagnosis of active asthma (within last 12 months) or current use of asthma medications (inhaled corticosteroids, leukotriene antagonists). Participants using bronchodilators will be allowed to participate
3. Second or third degree AV block or sinus node dysfunction
4. Known or suspected right to left sided cardiac shunts
5. History of a bleeding diathesis
6. History of clinically overt stroke within the past 3 years
7. History of severe hypertension not adequately controlled with anti-hypertensive medications (SBP \geq 200 mmHg and/or DBP \geq 110 mmHg)
8. Receiving chronic anti-coagulation or anti-platelet therapy
9. History of metastatic cancer
10. Receiving other investigational study agents, or have received a study agent in the last 30 days
11. Uncontrolled intercurrent illness including, but not limited to:
 - a. Ongoing or active infection
 - b. Symptomatic congestive heart failure
 - c. Unstable angina pectoris
 - d. Cardiac arrhythmia
 - e. Psychiatric illness/social situations that would limit compliance with study requirements
12. Pregnancy (must be excluded by a negative urine pregnancy test in all women of childbearing potential) or breastfeeding
13. Know HIV infection
14. Participants who have previously undergone a hematopoietic stem cell transplant
15. Participants who are taking medications that may interact with the investigational agent, including dipyridamole, aminophylline, and theophylline

16. Caffeine and theophylline may not be taken within 12 hours of starting regadenoson. Dipyridamole and aminophylline may not be taken within 48 hours of starting regadenoson
17. Prior hypersensitivity reactions to either regadenoson or ultrasound contrast agents

3.2 Sickle Cell CEU Subject Eligibility Criteria:

Sickle Cell CEU Subject Inclusion Criteria:

1. Diagnosis of sickle cell disease confirmed by hemoglobin analysis

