4.5 Sickle Cell Control subjects (Milwaukee): To learn about the impact of CEU technique and definity microbubbles on the rise in microvascular blood flow rate, we will obtain skeletal muscle and myocardial contrast-enhanced ultrasound values from up to 20 sickle cell subjects. These subjects will follow the study procedure similar to regadenoson arm, however they will not receive regadenoson, hence acting as sickle cell control subjects. The 24 hr and 30 hr CEU studies will be optional for these subjects.

The subjects who have already completed Regadenoson arm or Sickle Cell CEU Arm of the study may also be enrolled in this arm. Likewise, subject may participate in the Regadenoson or Sickle Cell CEU Arm after completed participation in the 'Sickle Cell Control' Arm, if they meet study entry criteria for the respective Arm.

Blood Samples for Definity complement deposition (Milwaukee and Chicago):

To gather more valuable information about the mechanism for pain and other adverse events to contrast agents, such as Definity, we would like to collect blood samples from up to 14 subjects with sickle cell and up to 10 healthy controls, study-wide. Subjects with sickle cell and healthy controls who provide their consent will have a one-time blood sample while at their baseline state (see definition in **Section 3.7**), which will be used to evaluate complement deposition on study contrast (Definity) microbubbles. Labs for clinical complement values (C3, C4, CH50) will also be obtained. This may be a standalone blood draw or performed at another scheduled study visit. If this sample is drawn, the total volume of blood drawn for the study from any subject will not exceed 50ml per 8 week period.

Individuals who meet basic study entry criteria for any of the study arms (excluding the Technique Optimization Controls Arm), or subjects who previously participated in the study, may be approached for providing this sample. Of note, self-reported health status, (including sickle cell, pregnancy state, or other) may be allowed in evaluating eligibility for obtaining this blood sample, however should be confirmed via applicable screening procedures (Section 5), if the individual should go on to participate in other study arms.

5. Screening Procedures

*Screening evaluations are to be conducted within 30 days prior to start of protocol therapy (regadenoson, sickle cell CEU subjects, healthy controls, sickle cell controls, or technique optimization control subjects).

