6.5 Sickle Cell Control Subject

Sickle Cell Control Subject (0 hour):

- Signal Averaged ECG (+/- 30 days from infusion visit date)
- Reconfirm eligibility and that subject is at baseline (if necessary)
- Concomitant medication use reviewed
- Vital signs
- Limited functional 2D echocardiogram
- Contrast-enhanced ultrasound is performed
- Documentation of pain score prior to lab draw
- Correlative laboratory studies and optional “red and white blood cell” exploratory study labs are drawn
- Study lab draw for Definity complement deposition and values (optional)
- Complete cardiac questionnaire (can be completed any time prior to the end of the 24 hr CEU study)

Sickle Cell Control Subject (6 hours +/- 2hr from baseline):

- Vital signs
- Contrast-enhanced ultrasound
- Documentation of pain score prior to lab draw
- Correlative laboratory studies are drawn

Sickle Cell Control Subject (24 hours +/- 2hr from baseline –optional):

- Vital signs
- Contrast-enhanced ultrasound
- Documentation of pain score prior to lab draw
- Correlative laboratory studies and optional “red and white blood cell” exploratory study labs are drawn

Sickle Cell Control Subject (30 hours +/-2hr from baseline - optional):

- Vital signs
- Contrast-enhanced ultrasound
- Documentation of pain score prior to lab draw
- Correlative laboratory studies are drawn

Table 1. Study Schedule of Procedures for Regadenoson Subjects

Procedure	Screening	Baseline	6 hours (+/-2hr)	24 hours	30 hours (+/-2hr)	30 Day Follow up
Documentation- MedHx, medications, Tx & clinical data	X					
Signal-average ECG	X ^f					
PT/INR, PTT	X					
β-HCG ^c	X					
CBC	X					
Comprehensive metabolic panel ^b	X ^b					
VS (including SBP, HR, O ₂ sat)	X	X ^a				
Regadenoson infusion		X ^j				
Adverse event evaluation	X					
Limited functional 2D Echo		X		X		
Contrast-Enhanced Ultrasound		X	X	X	X	
iNKT cell measurement		X	X	X ^d	X	
Inflammatory Markers		X		X		
Exploratory “red and white blood cell” study labs ^g		X ^{h,i}		X ^{h,i}		
Definity complement deposition blood sample (optional)	X ^{i, k}					
Complement (C3, C4, CH50) (drawn if optional Definity complement sample drawn)	X ^{i, k}					
Pain Scores ^e	X	X	X	X	X	
Cardiac Questionnaire		X				
Coordinator calls subject weekly to assess for toxicities after regadenoson infusion						

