7.5 Compatibility

No formal pharmacokinetic drug interaction studies have been conducted with Lexiscan.

Effects of Other Drugs on Regadenoson

- Methylxanthines (e.g., caffeine and theophylline) are non-specific adenosine receptor antagonists and may interfere with the vasodilation activity of regadenoson. Patients should avoid consumption of any products containing methylxanthines as well as any drugs containing theophylline for at least 12 hours before regadenoson administration. Aminophylline may be used to attenuate severe or persistent adverse reactions to regadenoson.
- In clinical studies, regadenoson was administered to patients taking other cardioactive drugs (i.e., β -blockers, calcium channel blockers, ACE inhibitors,

nitrates, cardiac glycosides, and angiotensin receptor blockers) without reported adverse reactions or apparent effects on efficacy.

- Dipyridamole may change the effects of regadenoson. When possible, withhold dipyridamole for at least two days prior to regadenoson administration.

Effect of Regadenoson on Other Drugs

Regadenoson is not known to inhibit the metabolism of substrates for CYP1A2, CYP2C8, CYP2C9, CYP2C19, CYP2D6, or CYP3A4 in human liver microsomes, indicating that it is unlikely to alter the pharmacokinetics of drugs metabolized by these cytochrome P450 enzymes.

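### Caffeine is restricted before and during the regadenoson visit, but the sickle cell control procedures neither restrict nor record it, so visit conditions differ between the arms by more than the drug

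*Combined protocol and SAP*

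**What the plan says.** For the regadenoson arm, the exclusion criteria in section 3.1 state: "Caffeine and theophylline may not be taken within 12 hours of starting regadenoson". Sections 5.1 and 6.1 repeat the check at screening and on the day, and allow the infusion to be delayed if the condition is not met. Section 6.1 then extends the condition through the visit: "Caffeine may not be ingested during the infusion or observation period".

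Section 7.5 gives the pharmacological reason: "Methylxanthines (e.g., caffeine and theophylline) are non-specific adenosine receptor antagonists". The same sentence goes on to say that they may interfere with the drug's vasodilating action.

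For the sickle cell control arm, section 4.5 states: "These subjects will follow the study procedure similar to regadenoson arm, however they will not receive regadenoson". It gives the arm's purpose as learning how far CEU technique and the microbubbles contribute to the rise in flow. It makes the 24-hour and 30-hour scans optional. It also allows one person to take part in both arms at different times, if eligible.

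**The concern.** A control arm that repeats the treated visit without the drug is useful to the extent that everything else about the visit is the same. Caffeine intake is one visit condition that the protocol fixes tightly in one arm and leaves open in the other. By the protocol's own account, the substance acts on adenosine receptors, the receptor family under study.

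If flow rises in treated subjects and not in controls, or rises in both, the reader will want to say what that implies about the drug as against the imaging procedure. With caffeine exposure unequal by rule and unrecorded, that reading carries an alternative explanation that cannot be examined afterwards. Enrolling the same person in both arms does not remove it: stable differences between people cancel, but a difference in visit conditions does not.

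**Working it through.** The plan states no figure on this point, so there is nothing to reproduce. The check is a comparison of the text by arm, plus simple arithmetic on hours.

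**Step 1. Rules side by side.**

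| Stage | Regadenoson arm | Sickle cell control arm |
|---|---|---|
| Eligibility (3.1 v 3.5) | 12-hour exclusion | No caffeine item |
| Screening (5.1 v 5.5) | "Determine caffeine and theophylline will not be taken 12 hours prior to receiving regadenoson" | "Collection of demographics, race, ethnicity, medical diagnostic history and medication history", with vital signs, height and weight, and a pregnancy test; no caffeine item |
| Day of visit (6.1 v 6.5) | "Assess caffeine and theophylline intake for previous 12 hours", with a delay rule | "Concomitant medication use reviewed", with no sub-item |
| During visit (6.1 v 6.5) | Barred through infusion and observation | No caffeine item |
| Schedule (Table 1 v Table 5) | No caffeine row | No caffeine row |

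The tables do not carry the rule for either arm. The difference lies in the text: the regadenoson arm has it at four points and the control arm at none.

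**Step 2. Does section 4.5 carry the rule over?** Section 6.5 is a step-by-step list that follows 6.1 closely; its ECG line even keeps a reference to an infusion visit. It retains the medication-review step but drops the caffeine and theophylline sub-item that sits under that step in 6.1. A coordinator working from 6.5 is not told to restrict caffeine or to ask about it. A general statement of similarity does not restore an item that the detailed list omits.

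**Step 3. Minimum caffeine-free time at each CEU under the written rules.** Inputs: 12 hours before infusion start (3.1); baseline CEU within 4 hours before infusion; 6-hour scan ±2 hours; 24-hour scan within two hours before the infusion stops; 30-hour scan ±2 hours (all 6.1). Formula: 12 hours plus the scan time relative to infusion start.

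| Scan | Regadenoson arm | Controls |
|---|---|---|
| Baseline | 12 − 4 = 8 to 12 − 0 = 12 h | 0 h |
| 6 h | 12 + 4 = 16 to 12 + 8 = 20 h | 0 h |
| 24 h | 12 + 22 = 34 to 12 + 24 = 36 h | 0 h (scan optional) |
| 30 h | 12 + 28 = 40 to 12 + 32 = 44 h | 0 h (scan optional) |

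The written restriction ends with the observation period, at 12 + 24 + 6 = 42 hours. The last two hours of the 30-hour range therefore apply only if observation is extended to the scan. Section 6.1 lets the post-baseline scans be done earlier at the study physician's discretion and lets the infusion run over by up to 1 hour. Either would move these figures, but not the contrast between the arms.

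The control column is what the text guarantees, not what controls actually do.

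**Step 4. Which analysis is touched?** Sections 14.1.1 and 14.2 define the primary outcome as the change from baseline to 24 hours within the regadenoson arm. Section 14 does not mention the sickle cell control arm and specifies no comparison with it. The caffeine intake of controls therefore cannot enter the primary test. It bears only on the interpretive use of the arm set out in section 4.5.

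**The case against.** The strongest reply is that the rule is about the drug. Section 7.5 presents it as a drug interaction, and the eligibility criteria list it alongside theophylline, dipyridamole and aminophylline. Controls receive no drug, so on this view they need no rule. Nothing in the documents says that caffeine changes CEU flow in someone not given regadenoson. This stands as a limit on what can be claimed. It does not answer the point about matched conditions, because the arm's stated design is the treated procedure without the drug.

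Four further replies have weight:

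- No between-arm test is planned. This is correct, and it confines the point to descriptive interpretation.
- The medication review kept in 6.5 could prompt a question about caffeine. It could, but a review of medication need not capture a dietary substance, and nothing requires it to be written down.
- If a control's caffeine intake is much the same at each scan, much of any effect on the level of flow would cancel in the change from baseline. This is true, and without a record it cannot be checked.
- Caffeine is not the only difference. Eligibility differs between 3.1 and 3.5, and the later control scans are optional. This is also true, but those differences are written down, whereas caffeine exposure in controls would be unknown.

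A reader might infer that part of any difference between the arms is due to caffeine, or try to express that part as a share of the planned rise from 0.7 to 1.0. The documents do not support this. They give no size or direction for such an effect, which could inflate or mask a difference. The planned rise is also a within-arm target, not a between-arm one. Nor can one say how many controls are affected: 20 is an enrolment ceiling, the number having the optional scans is unknown, and so is their intake.

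**Conclusion.** The point holds in a limited form. Caffeine is restricted by rule for 42 hours in the regadenoson arm. It is neither restricted nor recorded in the control arm that is meant to mirror it. The primary within-arm result is unaffected.

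What is weakened is the use of the controls to separate a drug effect from effects of CEU technique and microbubbles, because the visits differ by more than the drug. The size of any consequence cannot be stated from the documents.

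The conclusion rests on reading 6.5 as the operative instruction for controls. If site practice already applies the same caffeine conditions to them, only the wording and the missing record need attention. This is a cheap improvement, not a defect in the main analysis.

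**What to change.** 1. Reconcile sections 4.5, 6.1 and 6.5 and Table 5 so that the same caffeine conditions hold at CEU visits in both arms, and say so explicitly.
2. Record the time of last caffeine at each CEU in both arms. Any descriptive comparison of the arms can then include a sensitivity analysis by caffeine exposure.
3. For controls already scanned without a record, state the limitation when the arm is reported.

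The cost is a line of text in 6.5, an entry in Table 5 and one case report form field. If the existing condition is extended to controls, the burden depends on how long they stay: at nominal scan times, 12 + 6 = 18 hours without caffeine for those having only the 6-hour scan, and up to about 42 hours for those who stay for the optional 30-hour scan. That could make the optional scans slightly less attractive.

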11.1 Adverse Event Monitoring

11.1.1 Study Staff

Information on all adverse events, whether reported by the subject, directly observed, or detected by physical examination, laboratory test or other means, will be collected, recorded, followed, and reported as described in the following sections.

The PI will monitor and review adverse events monthly or more often as needed.

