11.2 Definitions

Adverse Event (AE) – Any untoward or unfavorable medical occurrence in a human subject, including any abnormal sign (for example, abnormal physical exam or laboratory finding), symptom, or disease, temporally associated with the subject's participation in research, whether or not considered related to the subject's participation in research.

Serious Adverse Event (SAE) – Any adverse event temporally associated with the subject's participation in research that meets any of the following criteria:

- Results in death;
- Is life-threatening (places subject at immediate risk of death from the event as it occurs);
- Requires inpatient hospitalization or prolongation of existing hospitalization, within 48 hours of a CEU or other research-related activity (*see below);
- Results in a persistent significant/incapacity;
- Results in a congenital anomaly/birth defect; or
- Any other adverse event that, based upon appropriate medical judgment, may jeopardize the subject's health and may require medical or surgical intervention to prevent on the other outcomes listed in this definition

Note that seriousness and severity are separate concepts. The term "severe" refers to the intensity of a specific event; a severe event may be of minor medical significance (e.g., a severe leg cramp). The term "serious" is based on an outcome or action criteria that are usually associated with events that pose a threat to the patient's life or functioning. An event that is mild in severity is serious if it leads to one of the outcomes defined above.

Grade 4 and 5 events will always be considered Serious Adverse Events. Many Grade 3 and some Grade 1 and 2 events may meet the definition of a Serious Adverse Event.

* Individuals with sickle cell disease are not uncommonly hospitalized for sickle cell-related ailments, such as pain exacerbations or others, which are part of the disease process. It is important to note that any adverse event should be assessed with regard to activities that are related to research.

- **SAE's which originate from a study-related intervention, such as CEU, are most likely to occur immediately and the PI should acknowledge all hospitalizations, perceived prolongation of hospitalizations or ED visits, which occur within 48 hours of a study intervention being performed.**

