11.4 Recording Adverse Events

Participating investigators will assess the occurrence of AEs and SAEs at all participant evaluation time points during the study. All AEs and SAEs whether reported by the participant, discovered during questioning, directly observed, or detected by physical examination, laboratory test or other means, will be recorded in the participant's study and/or medical record and on the appropriate study-specific case report forms (CRFs).

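### Section 11.2 makes a hospitalisation within 48 hours of a CEU a serious adverse event, but the contrast-only arms have no planned step to find such events after the last scan

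*Combined protocol and SAP*

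**What the plan says.** The SAE definition in Section 11.2 includes this criterion: "Requires inpatient hospitalization or prolongation of existing hospitalization, within 48 hours of a CEU or other research-related activity". The accompanying note says that "SAE's which originate from a study-related intervention, such as CEU, are most likely to occur immediately", and that "the PI should acknowledge all hospitalizations, perceived prolongation of hospitalizations or ED visits, which occur within 48 hours of a study intervention being performed". It gives no method for finding them.

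On collection, Section 11.4 states: "Participating investigators will assess the occurrence of AEs and SAEs at all participant evaluation time points during the study". Section 11.1.1 is broad about sources: "Information on all adverse events, whether reported by the subject, directly observed, or detected by physical examination, laboratory test or other means" is to be collected and recorded. Section 11.6.1 foresees that an investigator may learn of an SAE late because the participant was treated elsewhere, and starts the 24-hour reporting clock when the investigator learns of it.

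On contact after scanning, Section 6.1 provides for the regadenoson arm: "Subjects will be contacted by phone weekly (plus or minus 3 days) for 4 weeks following the conclusion of regadenoson therapy". The stated purpose is "to assess for any potential toxicities related to study drug". Sections 6.2 to 6.5 and Tables 2 to 5 contain no equivalent; in each, the last listed activity is a scan visit. For Sickle Cell Controls, Section 4.5 adds: "The 24 hr and 30 hr CEU studies will be optional for these subjects".

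**The concern.** The protocol sets a 48-hour window and a duty to know what happened in it, while tying event assessment to evaluation time points. In the contrast-only arms the last time point is the last scan, so an assessment made there cannot cover the hours that follow. After that, an admission or ED visit reaches the study team only if the subject reports it or the team comes across it.

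Contrast safety is a live question in this study. The background section reports pain events in 4.1% (4/97) of CEU exams in the team's own sickle cell patients, against a reported 1.2% for Definity, and a secondary objective concerns contrast-associated pain. Section 12.2 asks the DSMB to review event rates and to monitor the safety of diagnostic procedures as well as treatments. If post-scan events in most of the scanned groups depend on being volunteered, the counts given to the DSMB could be too low, and they would not be gathered in the same way as those from the regadenoson arm.

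**Working it through.** The point concerns ascertainment. The plan states no figure to reproduce, so the check sets the visit schedules against the 48-hour rule.

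**1. What follows the last scan in each arm** (Sections 4.1 to 4.5 and 6.1 to 6.5; Tables 1 to 5)

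| Arm | Slots | After the last scan | After earlier scans |
|---|---|---|---|
| Regadenoson | 27 | Weekly calls for 4 weeks | Continuous stay to 30 h |
| Sickle Cell CEU | 30 | Nothing planned | Second baseline 7 to 30 days later, if feasible; crisis scan done during an admission |
| Healthy Control | 20 | Nothing planned after day 30 | Day 1 visit follows day 0; day 30 visit follows day 1 |
| Technique Optimization | up to 20 | Nothing planned | Optional second scan at least a day later |
| Sickle Cell Control | up to 20 | Nothing planned; 6 h is the last required time point | 24 h and 30 h scans, if the subject opts in |

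Tables 2 to 5 each carry an adverse event evaluation row. In Table 4 it is marked at the two measurements only. In Tables 2, 3 and 5 a single mark appears, probably a merged cell flattened in reading, so its column position is not used here. None of these tables has a column after the last scan.

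**2. Size of the group**

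- Contrast-only slots: 30 + 20 + 20 + 20 = 90 at most.
- Share of all CEU slots: 90 / (90 + 27) = 90/117 = 77%.
- Counting only the two arms with a fixed size: 50 / (50 + 27) = 50/77 = 65%.

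These are enrolment slots. Section 4.5 lets one person take part in more than one arm, so the number of individuals may be smaller.

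**3. Does the regadenoson arm cover the window?**

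- Assume the first weekly call is due at day 7. With 3 days either way it falls on day 4 to 10 after the infusion ends, or 96 to 240 hours.
- The last scan is nominally at 30 h, about 6 hours after a 24-hour infusion ends. Its 48-hour window closes at about 6 + 48 = 54 hours after the end of infusion.
- The earliest call is therefore later than the end of the window. The call can reach the window only by recall, and its stated subject is study-drug toxicity, not CEU events.

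**4. Would clinic records fill the gap?** Section 3.6 recruits the sickle cell subjects from the centre's own clinic, so some admissions would probably be visible to the team; that is an inference, and no section requires a record check. Up to 20 + 20 = 40 of the 90 slots are healthy or technique controls recruited by advertisement, including at blood donor centres, whom sickle cell clinic records need not cover.

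**The case against.** The strongest reply is that event collection in these arms is far from absent. Section 11.1.1 accepts reports from any source, Section 11.4 requires assessment at every time point, and Section 11.6.1 provides for events learned of late. Several scans are followed by another visit, and pain-crisis scans are done in hospital. The study physician may also be the treating physician (Section 3.7). The protocol expects CEU-related SAEs to be immediate, when the subject is still present.

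Much of this stands, and it limits the point. A reader might infer that the 48-hour criterion cannot be applied in these arms. The documents do not support that: it is a classification rule and applies to any event the team learns of. Nor are the regadenoson calls a clean standard that the other arms fail to meet, as step 3 shows.

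What the reply does not supply is a planned step after the last scan. Late-awareness wording governs reporting once an event is known; it does not find the event. The remark on timing says most likely, not always, and the same note still sets a 48-hour window.

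**Conclusion.** The point holds as a gap in ascertainment. For up to 90 contrast-only slots (77% of 117 at full enrolment), detection after the last scan is passive and unspecified, so CEU-related hospitalisations and ED visits could be under-counted. The regadenoson arm covers the same window by recall only. This rests on reading Sections 6.2 to 6.5 and Tables 2 to 5 as complete lists of planned contacts. It is a cheap improvement to safety data and does not bear on the primary endpoint.

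Three further inferences are tempting but unsupported:

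- **A numerical bias.** The documents give no proportion of events that would be volunteered, and Section 14 plans no confidence limit on an admission rate. The 4.1% concerns pain per exam, not admissions.
- **A fixed number of unobserved hours.** This depends on which scan starts the clock, which optional scans are done, and whether the last scan is inpatient.
- **A failed safety comparison.** Sections 4.2 to 4.5 give these arms purposes of measurement variability, technique and blood flow. None is planned as a contrast-only safety reference for regadenoson.

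**What to change.** Amend Sections 6.2 to 6.5 and Tables 2 to 5 to add one scripted contact 48 to 72 hours after the last CEU of each visit series, asking about new pain, ED visits and admissions. For inpatient scans, use a chart check instead. Ask the same CEU question at the first regadenoson call, so that every arm is asked the same thing. Tabulate the answers per CEU exam by arm for the DSMB.

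The cost is a short amendment and coordinator time:

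- One call per series, with two series for healthy controls (days 0 and 1, then day 30): 30 + 2 × 20 + 20 + 20 = 110.
- If all 30 Sickle Cell CEU subjects have a second baseline and all 20 technique controls a second scan: 110 + 30 + 20 = 160.
- Red cell exchange scans in up to 2 subjects would add a few at most.

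For comparison, 27 × 4 = 108 calls are already planned in the regadenoson arm. The burden on subjects is one short call per series.
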